## 2.0 Objectives

**3.1 Primary Objective:** The primary objective is to estimate the 1-week change in the proportion of HCV-infected hepatocytes in participants with HCV mono-infection and HIV/HCV coinfection on therapy with two or three DAAs with different mechanisms of action using single cell laser microdissection (scLCM).

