### 3.2 Secondary Objectives:

3.2.1. Estimate the change over the first week in plasma HCV RNA in subjects with HCV mono-infected and HIV/HCV co-infected participants on therapy with two or three DAAs

3.2.2. Estimate the 1 week change in the amount of HCV RNA per infected hepatocyte using scLCM on liver biopsy specimens, obtained just prior to treatment initiation (pre-treatment), and after the first week of DAA therapy.

3.2.3. Estimate the change in the proportion of HCV-infected hepatocytes that express interferon-stimulated genes (ISGs) within the first week of DAA therapy using scLCM.

3.2.4. Measure the change in expression of ISGs in non-parenchymal intrahepatic immune cells (Kupffer cells, plasmacytoid dendritic cells) within the first week of DAA therapy using scLCM.

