### 3.3 Exploratory Objectives:

3.3.1. Estimate the 1 week change in expression of ISGs from peripheral blood mononucleated cells (PBMCs) within the first week of DAA+RBV therapy using scLCM.

3.3.2. Compare sequence(s) of HCV protease, nonstructural protein 5A (NS5A), and nonstructural protein 5B (NS5B) depending on the peripheral sequence) of intrahepatic HCV RNA in single cells and bulk tissue, before and during week 1 of DAA+RBV therapy.

3.3.3. Estimate the week 1 change in the sizes and numbers of HCV-infected clusters on DAA therapy to test whether clearance of HCV-infected hepatocytes occurs in spatially random patterns or within specific clusters.

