## 10.0 Sample Size

The anticipated sample size for analyses is 15 participants with 5 in each of three distinct groups. Group C will enroll 5 patients with HIV/HCV genotype 1a coinfection and will receive treatment with SOF/VEL representing inhibitors of HCV NS5B and NS5A a. Group A and B will

each enroll 5 patients with HIV genotype 1a mono-infection; Group A will be treated with SOF/VEL/VOX and Group B will receive only SOF/VEL representing inhibitors of HCV NS5B and NS5A only. As such, Groups B and C are treated with same two-drug DAA regimen and will permit the comparison of persons with HIV/HCV and HCV. In contrast, Groups A and B include patients with HCV mono-infection and differ by the use of the HCV NS3/4 inhibitor Voxilaprevir in Group A and will permit the comparison of the NS3/4 inhibition versus none.

Because this study is exploratory and is enrolling a very small sample, traditional statistical power calculations are not being used to justify the sample size. Instead, this sample size was developed based on the feasibility of both anticipated enrollment and the feasibility of the laboratory procedures, namely single cell laser microdissection.

For the primary outcome of difference in proportion of HCV-infected hepatocytes between week 1 and baseline, we present an approximate confidence interval around the difference in proportion within subject to show the level of precision in this exploratory single-arm study. The following assumptions are made to approximate the confidence interval in a conservative way:

- for within-subject variation – proportion of infected hepatocytes at any particular time-point is 50% (this assumption is conservative as results in maximum variation),
- the number of hepatocytes measured within each subject is 400 (this is conservative as it is estimated that between 400 and 1000 hepatocytes will be measured),
- normal approximation to the binomial for standard error estimation, and the variance of the difference will be approximated as twice the variance (assuming independence between week 1 and baseline, which is conservative except under negative correlation, which is not expected given the reported potency of the intervention being studied).

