These assumptions give an estimated within-subject standard error of 0.035 for the primary outcome and can be used to formulate a confidence interval on the difference in proportions of HCV-infected hepatocytes between week 1 and baseline on a single individual. For other less conservative assumptions (larger number of hepatocytes sampled, or estimated proportion of HCV-infected hepatocytes being either larger or smaller than 0.5 at either week 1 or week 0), the within subject standard error for the difference in proportions outcome would be smaller than 0.035, and so this represents the maximum standard error for the given assay parameters that specify that at least 400 hepatocytes will be measured in each subject at each time point.

For combining the estimated differences across subjects in order to obtain a study sample estimate for the difference in proportion of HCV positive hepatocytes between week 1 and baseline, the average difference across the 5 subjects within each group will be calculated. Assuming independence across individuals, and using the above maximum within subject standard error for each of the 5 subjects gives a standard error for the average as  $0.035/\sqrt{5}$ , which is 0.015. This was obtained using conservative assumptions for the purpose of sample size considerations in this exploratory study. Therefore, the estimated maximum half-width of a two-sided 95% confidence interval on the study sample average difference in proportion is approximately  $1.96 \times 0.015 = 0.031$ .

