## 11.0 Statistical Analyses Plan:

All outcomes will be summarized and described with appropriate summary statistics. For example, estimated binomial proportions (e.g., for % of HCV-infected hepatocytes) will include 95% confidence intervals. Means, medians for continuous outcomes will include confidence

intervals and key percentiles (eg, 25th, 75th percentiles), respectively. Outcomes defined as changes will also present summary distribution of values at each time point contributing to change outcome. In addition, because of small sample size, outcomes will also be summarized on a per-subject basis for reporting. Changes will be defined as absolute differences for those outcomes where baseline distribution of proportion is close to 0 or 1, and relative (and absolute secondarily), changes otherwise. For continuous outcomes, both absolute and relative changes from baseline will be explored and summarized. Confidence intervals (using exact methods) on change outcomes will be calculated and presented.

For the primary outcome, the estimated differences will be summarized and described on a per-subject basis (i.e. 15 differences and intra-subject confidence intervals). Additionally, the proportion of infected hepatocytes will be summarized across subjects at each time point and presented. Finally, the average difference from week 0 to week 1 (absolute difference) for the study sample will be estimated and summarized.

For the plasma VK secondary outcome, longitudinal modeling will be used to combine plasma HCV viral loads (VL) over the first week. For instance, marginal modeling will focus on estimation of levels across the study sample (ie, population level inference). This can be used to describe the average change in HCV VL over the first week on treatment. In addition, (generalized linear) mixed effects models will focus on subject-specific inference (ie, prediction). Since this is a small study, these data will be graphically represented by subject.

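### The primary 1-week change averages Day-7 and Day-4 biopsies: only 3 of the 5 participants per arm are biopsied at one week

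*Combined protocol and SAP*

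**What the plan says.** The Synopsis and Section 7.1 place the first nine participants in Cohort 1 (3 per arm) and the next six in Cohort 2 (2 per arm). Section 7.2 and the footnotes to Table 4 give each participant a Day 0 biopsy and one on-treatment biopsy, on Day 7 for Cohort 1 only or Day 4 for Cohort 2 only.

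The outcome definitions do not reflect this split:

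- Section 2.0, item 3.1: "The primary objective is to estimate the 1-week change in the proportion of HCV-infected hepatocytes".
- Section 10.0 opens its precision argument with "For the primary outcome of difference in proportion of HCV-infected hepatocytes between week 1 and baseline". It then says that "the average difference across the 5 subjects within each group will be calculated", and gives 0.031 as "the estimated maximum half-width of a two-sided 95% confidence interval on the study sample average difference in proportion".
- Section 11.0 expects "15 differences and intra-subject confidence intervals" and ends the primary analysis with "Finally, the average difference from week 0 to week 1 (absolute difference) for the study sample will be estimated and summarized".
- Secondary objective 3.2.2 uses biopsies "obtained just prior to treatment initiation (pre-treatment), and after the first week of DAA therapy". Exploratory objective 3.3.3 reads "Estimate the week 1 change in the sizes and numbers of HCV-infected clusters on DAA therapy".

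Objectives 3.2.3 and 3.2.4 are worded to cover any time within the first week, so Day 4 fits them.

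**The concern.** Only nine participants can supply a Day-0-to-Day-7 change, yet the plan counts fifteen and averages five per arm. Nothing in Sections 10 or 11 says how a Day-4 biopsy becomes a week-1 value. Followed literally, the headline estimate is a mixture of two time points labelled as one. The precision quoted for it belongs to five pairs, not to the three biopsied at one week.

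This matters because the study's stated aim is estimation, and one week is also the time point of hypotheses 2.1 and 2.2 in Section 1.0. Section 4.2 justifies the Day-4 biopsy on the ground that infection falls quickly and an earlier look helps to model its elimination from the liver. The design therefore treats the two days as different, while the analysis treats them as interchangeable. The longitudinal modelling in Section 11 is for plasma only.

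**Working it through.** **1. Reproducing the plan's figure.** Section 10 assumes an infected proportion of 0.5, 400 hepatocytes per participant per time point, and independence between time points.

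- Within-subject SE = sqrt(2 × 0.5 × 0.5 / 400) = 0.0354 (plan: 0.035).
- SE of the mean of 5 = 0.0354 / sqrt(5) = 0.0158 (plan: 0.015, which is truncated).
- Half-width = 1.96 × 0.0158 = 0.031, as stated. The plan's printed product, 1.96 × 0.015, would be 0.029; 0.031 comes from the unrounded values.

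**2. Same formula, by biopsy day.** Half-width = 1.96 × 0.0354 / sqrt(n).

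| Set | n per arm | Half-width per arm | n, all arms | Half-width, all arms |
|---|---|---|---|---|
| Mixed, as planned | 5 | 0.031 | 15 | 0.018 |
| Day 7 | 3 | 0.040 | 9 | 0.023 |
| Day 4 | 2 | 0.049 | 6 | 0.028 |

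These figures count cell-sampling error only. The Day-7 half-width is 29% wider than the stated one (0.040 / 0.031).

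**3. Bias of the mixed average.** Let p0, p4 and p7 be the mean infected proportions at Days 0, 4 and 7, with p0 equal in the two cohorts. The planned mean is (3/5)(p7 − p0) + (2/5)(p4 − p0) = (p7 − p0) + 0.4 × (p4 − p7). The 1-week fall is understated by 0.4 × (p4 − p7) whenever p4 exceeds p7.

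**4. Illustration, log-linear decline (assumed).** The baseline of 21–45% is from Sections 4.1 and 8.8. The 1% at Day 7 is from Section 4.2, in two coinfected participants on another regimen. Then p4 = p0 × (p7/p0)^(4/7).

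- p0 = 0.21: p4 = 0.037; bias = 0.4 × (0.0369 − 0.01) = 0.011, or 5.4% of the 0.20 fall.
- p0 = 0.45: p4 = 0.051; bias = 0.4 × (0.0511 − 0.01) = 0.016, or 3.7% of the 0.44 fall.

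**5. Precision on these same inputs.** The variance per pair is v = [p0(1 − p0) + pt(1 − pt)] / 400.

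- Five mixed pairs: 1.96 × sqrt((3·v7 + 2·v4)/25) = 0.019 (p0 = 0.21) and 0.023 (p0 = 0.45).
- Day 7: 1.96 × sqrt(v7/3) = 0.024 and 0.029.
- Day 4: 1.96 × sqrt(v4/2) = 0.031 and 0.038.

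**6. Sensitivity of the bias.**

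- No decline shape assumed, 1% at Day 7: the bias is 0 at a Day-4 level of 1%, 0.4 × 0.01 = 0.004 at 2%, 0.4 × 0.04 = 0.016 at 5%, and 0.4 × 0.09 = 0.036 at 10%.
- The bias reaches the stated 0.031 at a Day-4 level of 0.01 + 0.031/0.4 = 8.8%. Against the matched half-widths of 0.019–0.023 from step 5, it does so at about 5.7–6.7%.
- Assumed linear decline to 1%: p4 = 0.096 or 0.199, and the bias is 0.034 or 0.075, about 17% of the fall.

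**The case against.** The strongest defence is that week 1 can be read loosely. Section 7.2 describes the first seven days as one primary assessment and lists both biopsy days within it. Objective 3.3.1 uses a 1-week change and a change within the first week in the same sentence. On that reading, all fifteen differences are first-week changes. However, placing both biopsies in one study step does not make a Day-4 change a 1-week change. The hypotheses refer to one week after treatment, and Section 4.2 frames the regimen comparison at seven days. At best the outcome is ambiguous, and the average still mixes two times.

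Other points carry weight and limit the concern:

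- The mismatch may be older wording left in place when the second biopsy was moved for some participants. That would explain it, but the current text still needs reconciling.
- Section 11 reports each participant's difference and the proportions at each time point, and it allows summaries by category. A reader could separate the days. None of these summaries names cohort or corrects the average.
- The cohorts are 3:2 in every arm, so pooling does not confound the arms.
- The log-linear bias is smaller than the cell-sampling half-width on the same inputs. Between-subject spread is probably larger still: with an assumed SD of 0.08–0.12, the half-width for five participants is 1.96 × SD / sqrt(5) = 0.07–0.105.
- The choice between a Day-7 definition, cohort-specific changes and a model using both days rests with the sponsor. The plan must make that choice explicit.

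**Conclusion.** The concern holds and should be fixed. For 6 of 15 participants (40%), the primary outcome as defined cannot be observed, and the plan as written reports a Day-7/Day-4 mixture as the 1-week change. The stated 0.031 is a valid cell-sampling bound for the mean of any five pairs. It is not the precision of a week-1 change, which is 0.040 per arm on three participants by the plan's own formula.

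The size of the bias is uncertain because the documents give no Day-4 level. It is 0.011–0.016 under the log-linear assumption and 0.034–0.075 under a linear one, with equal mean baselines and 1% at Day 7 in both cases. The inconsistency and the half-widths do not depend on those assumptions. The study is exploratory, and no claim is made about power or type I error.

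**What to change.** Define the primary change by biopsy day, for example: the absolute change from Day 0 to Day 7 (Cohort 1, 3 per arm, 9 in total) is the 1-week change, and the change from Day 0 to Day 4 (Cohort 2, 2 per arm, 6 in total) is reported separately. Carry the same definition into objectives 3.1, 3.2.2 and 3.3.3 and into Sections 10 and 11. Do not label any average across both days as the week-1 change.

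Restate the Section 10 maximum half-width per arm as 0.040 (Day 7) and 0.049 (Day 4), noting that both count cell-sampling error only and leave out variation between participants. Any analysis of all 15 should account for biopsy day, for example through a model in time since first dose or by stratifying on cohort. Such a model would also serve the purpose for which Section 4.2 added the Day-4 biopsy.

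The cost is protocol and SAP wording plus minor programming, with no new participants, biopsies or visits. The drawback is that the stated precision becomes less favourable and the arm summaries rest on three and two participants.

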In addition, inhibition of the HCV protease may restore innate intra-hepatic immune functions that are thought to be impaired by the virus. In response to viral replication intermediates, such as viral RNA and proteins, IPS-1 and TRIF adaptor protein act as signaling intermediates in retinoic acid-inducible gene (RIG-I) and/or Toll-like receptor 3 (TLR3) pathways. Activation of these pathways induces IRF3 activation and subsequent transcriptional activation of type I interferons (IFN- $\alpha/\beta$ ) and interferon-sensitive genes (ISGs). Type I interferons and ISGs play a major role in combating viral infections. Cleavage of IPS-1 and TRIF by HCV NS3/4A blocks the downstream signaling pathway, resulting in inefficient activation of IRF3 and severely reducing the host innate immune response against the viral infection. It is possible that HCV protease inhibitors (PI) can play a dual role in countering viral infection through a direct antiviral mechanism, as well as by abrogating the HCV protease-mediated downregulation of innate immunity pathways, such as the RIG-I and TLR3 pathways.

The comparison of the intra-hepatic HCV kinetic and immunologic response after 7 days for dosing with SOF/VEL and SOF/VEL/VOX will permit the in vivo assessment of the role of protease inhibition on hepatic clearance of HCV during DAA treatment.

The change in the timing of the second biopsy is based on investigator review of unpublished, preliminary data from A5335s was presented at the Annual ACTG Network Meeting in June 2017. In this study, two participants with HIV/HCV coinfection underwent paired liver biopsies at day 0 and day 7 of treatment with paritaprevir/ritonavir/ombitasvir + dasabuvir. In both participants, the proportion of HCV-infected hepatocytes had decreased to only 1% (Figure 1). The rationale for the second liver biopsy at day 4 is that this earlier time point will allow better understanding of this rapid and profound reduction in HCV burden and allow for the more precise modeling of HCV elimination from the liver.

Figure 1: Proportion of HCV-infected hepatocytes at Day 0 and Day 7, A5335S

The vertical axis represents the number of HCV-infected hepatocytes counted by sLCM and the horizontal axis represents the HCV RNA production of each hepatocyte in IU/mL (one IU = two copies of HCV RNA) with zero (0) representing an uninfected hepatocyte.

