## **7.0 Study design and Schedule of Events**

This study is an open-label, partially randomized clinical trial.

Table 2: Protocol Schema

All subjects will receive a total of 12 weeks of HCV treatment with oral direct acting antiviral (DAA) therapy. The study will occur in four steps.

Cohort 1: Paired liver biopsies on Day 0 and Day 7

Antiretroviral therapy (HIV seropositive only)													
Step 1	Step 2							Step 3			Step 4		
Screening/ Randomization	SOF/VEL/VOX or SOF/VEL							SOF/VEL			Follow-up		
	Entry/D0	D1	D2	D3	D4	D5	D6	D7	WK4	WK8	WK12	WK16	WK24
	Liver BX	VK	VK	VK	VK				Liver BX	VK	VK	VK	VK
VK								VK					

## Cohort 2: Paired liver biopsies on Day 0 and Day 4

Antiretroviral therapy (HIV seropositive only)													
Step 1	Step 2							Step 3			Step 4		
Screening/ Randomization	SOF/VEL/VOX or SOF/VEL							SOF/VEL			Follow-up		
	Entry/D0	D1	D2	D3	D4	D5	D6	D7	WK4	WK8	WK12	WK16	WK24
	Liver BX	VK	VK	VK	Liver BX			VK	VK	VK	VK	VK	VK
VK													

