### 7.1 Step 1. Screening/ Randomization

Following informed written consent, participants will undergo screening procedures as per schedule of Events (Table 4).

The first nine subjects enrolled will be assigned to Cohort 1 as follows: 3 subjects in Arm A, 3 subjects in Arm B, and 3 subjects in Arm C. The subsequent six subjects will be enrolled into Cohort 2 as follows: 2 subjects in Arm A, 2 subjects in Arm B, and 2 subjects in Arm C.

Eligible participants who are coinfecting will be randomized before Entry/ Day 0. Randomization will occur for eligible monoinfected subjects with a 1:1 between SOF/VEL and SOF/VEL/VOX. Eligible subjects who are coinfecting will be non-randomly assigned to receive SOF/VEL. Subjects must enter Step 2 within 42 days of screening. Screening evaluations to determine eligibility must be completed within 42 days prior to entry, with the exception of IL28B, which can be pulled from historical records or performed during screening, and HCV genotype, which can be pulled from historical records up to 6 months before screening or performed at screening. Subjects may be rescreened at the PI's discretion. Laboratory parameters may be repeated as clinically necessary to be resulted within 30 days of Day 0 as required by Johns Hopkins.

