Intrahepatic HCV infection was studied intensively using scLCM and spatial statistical analysis in liver tissue from four subjects of the ALIVE study of injection drug users (IDUs) who had chronic genotype 1 infection. By dissecting > 1000 individual hepatocytes, the viroscape was uncovered in eleven separate grids (Figure 2), demonstrating clusters of HCV+ hepatocytes; 21-45% of all hepatocytes were infected. HCV vRNA was measured in each hepatocyte and ranged from 1 – 50 IU across all subjects with the majority of cells producing < 10 IU. This technology has been extended to allow HCV sequencing from individual hepatocytes. Moreover, IFN responses were measured in the same hepatocytes; in contrast to clustered HCV infection, a representative ISG, IFITM3, was found to have a scattered expression pattern that was neither directed toward nor away from HCV clusters. Indeed, few HCV+ hepatocytes expressed the ISG. These results suggest poor targeting of ISG expression to HCV-infected hepatocytes, and may partly explain persistence of HCV infection. Since HCV RNA amounts are the principal measures of effective DAA treatment, scLCM with high-resolution qPCR and spatial statistical analyses form a highly innovative approach to the study of intrahepatic HCV infection before and during HCV DAAs and to study the effect of HIV coinfection on the host response.

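### Section 10's 0.031 'maximum' half-width for a group's average change covers cell-sampling error only, and its n = 5 fits a week-1 change only if Day 4 and Day 7 biopsies are pooled

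*Combined protocol and SAP*

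**What the plan says.** Section 10.0 gives no power calculation. It offers a precision statement instead: "we present an approximate confidence interval around the difference in proportion within subject to show the level of precision in this exploratory single-arm study". The inputs are 50% infected cells at each time point, 400 cells per subject, and a variance of the difference equal to twice the single-time-point variance. The resulting 0.035 is described as the largest within-subject standard error for those assay parameters.

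The section then moves to the group: "the average difference across the 5 subjects within each group will be calculated", and "using the above maximum within subject standard error for each of the 5 subjects gives a standard error for the average as" 0.035/√5, printed as 0.015. It concludes that "the estimated maximum half-width of a two-sided 95% confidence interval on the study sample average difference in proportion is approximately" 0.031. The change is described throughout as week 1 against baseline, in line with the primary objective (item 3.1), a one-week change.

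The biopsy schedule differs by cohort. Section 7.1 states: "The first nine subjects enrolled will be assigned to Cohort 1 as follows: 3 subjects in Arm A, 3 subjects in Arm B", and likewise 3 in Arm C; their second biopsy is on Day 7. The next six subjects, 2 per arm, follow the Section 7.0 schema headed "Cohort 2: Paired liver biopsies on Day 0 and Day 4" and have no Day 7 biopsy.

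Section 11.0 plans fifteen per-subject differences with their own intervals, an average week-0-to-week-1 difference for the study sample, and intervals by exact methods on change outcomes.

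**The concern.** The word maximum is fair for one subject's counting error under the stated assumptions. It is then carried over to a confidence interval for a group average, where two things are missing.

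- **No between-subject term.** Patients' true changes will differ. An interval for the mean change in such patients must include that variation, and the Section 10.0 calculation has no term for it.
- **An n that does not match the stated time point.** Only three subjects per arm have the Day 7 biopsy that a week-1 change needs.

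This is the only group-level precision figure for the primary outcome. A reader who takes a group's average as an estimate for patients of that kind would read about 3 percentage points as the worst case. Section 11.0 does not say whether the cell or the subject is the unit for that average, so a cell-based interval could later be reported as if it described patients.

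**Working it through.** **Inputs.** From Section 10.0: p = 0.5 at both time points, 400 cells per time point, independent time points, 5 subjects per group, multiplier 1.96. From Section 7.1: 3 subjects per arm in Cohort 1 (Day 7) and 2 per arm in Cohort 2 (Day 4).

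**1. The plan's figure.**
- Within-subject SE = √(2 × 0.5 × 0.5/400) = 0.0354.
- SE of a 5-subject average = 0.0354/√5 = 0.0158.
- Half-width = 1.96 × 0.0158 = 0.031, which reproduces the plan's result.
- The printed chain does not close: 0.035/√5 is 0.0157, not 0.015, and 1.96 × 0.015 = 0.029. The slip is confined to the intermediate value.

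**2. Same formula, Day 7 subjects only.**
- 1.96 × 0.0354/√3 = 0.040.
- No assumption is needed beyond the plan's own. The result is above the stated maximum.

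**3. Adding between-subject variation.** Let SDb be the between-subject SD of the true change.
- Half-width = 1.96 × √((SDb² + 0.0354²)/5).
- At SDb = 0 this is 0.031. It is larger for every SDb above 0.
- The documents give no SDb. As an assumed range, SDb of 0.03, 0.05 and 0.10 gives 0.041, 0.054 and 0.093.
- Equivalently, 0.031 is exceeded once the total SD of observed subject-level changes (true variation plus counting error) passes 0.031 × √5/1.96 = 0.035.

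**4. Independence of cells.** Section 8.8 takes consecutive cells in 10 × 10 grids and describes earlier tissue as "demonstrating clusters of HCV+ hepatocytes; 21-45% of all hepatocytes were infected".
- Positive correlation within a grid inflates the counting variance by a design effect D, so the half-width is 0.031 × √D.
- The documents give no D. As an assumed range, D of 1.5, 2 and 3 gives 0.038, 0.044 and 0.054.

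**5. Exact methods at these sample sizes.**
- The smallest two-sided signed-rank p-value is 2/2⁵ = 2/32 = 0.0625 for n = 5, and 2/2³ = 2/8 = 0.25 for n = 3.
- Both exceed 0.05, so an exact signed-rank interval on subject-level changes cannot reach two-sided 95% for either n.

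**The case against.** **The document limits its own claim.** Section 10.0 introduces the calculation as a within-subject interval, ties the maximum to the assay parameters and attaches 0.031 to the study sample's average. On that reading 0.031 is a valid bound for the five people observed if their cells are independent. This stands, and the point is confined accordingly. But the text never says that patient variation is left out, and the reported clustering makes the independence condition doubtful.

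**Pooling may be intended.** Section 7.2 treats the first seven days as the primary assessment, with the second biopsy on Day 7 or Day 4. Section 11.0 counts fifteen differences, and Section 10.0 averages five per group. Together these suggest that n = 5 pools both cohorts, so 0.040 should be read as the value for a Day 7 average that the plan does not expressly say it will compute. What remains is that Section 10.0 does not state the pooling, while the objective names a one-week change.

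**The 50% assumption is generous.** If baseline is 21–45% (Section 8.8) and Day 7 is near 1% (Section 4.2, two coinfected participants on another regimen), the n = 3 counting half-width is lower:
- 1.96 × √((0.21 × 0.79 + 0.01 × 0.99)/400)/√3 = 0.024.
- 1.96 × √((0.45 × 0.55 + 0.01 × 0.99)/400)/√3 = 0.029.

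Both are below 0.031. This shows that the margin may be comfortable for counting error. It does not make 0.031 a maximum, since the plan's own worst case at n = 3 is 0.040 and patient variation is still excluded.

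**Section 11.0 is not silent.** A reader might infer that it says nothing about intervals for changes. It does: it promises intervals by exact methods. What it leaves open is which exact method and which unit apply to the average.

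**Conclusion.** The point holds in a limited form. The 0.031 is correctly computed as cell-sampling error for five observed subjects with independent cells. It is not a maximum for a mean generalised to patients. For the three Day 7 subjects per arm, the same worst-case formula gives 0.040. The n = 3 result and the rounding slip need no assumed SD. The statement about generalising needs only that patients' changes differ, with counting error at its stated maximum.

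Three stronger readings are not supported.
- **That 0.031 is several times too small.** Any such multiple depends on an SD of change that the documents do not give.
- **That the sample size is wrong.** N was set by feasibility, power calculations are expressly set aside, and no planned test or decision uses 0.031.
- **That the plan claims this precision for the comparisons between groups.** It attaches 0.031 only to a single average.

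The defect is a mislabelled precision figure and an unstated unit of analysis. It is worth correcting because it is cheap to do. Per-subject reporting, already planned, limits the harm.

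**What to change.** **Section 10.0**
- Delete the word maximum for the group average. Label 0.031 as cell-sampling error only, for the subjects observed and assuming independent cells.
- State whether n = 5 pools Day 4 and Day 7 changes, and give 0.040 for the Day 7 change at n = 3.
- Print the chain as 0.0354/√5 = 0.0158 and 1.96 × 0.0158 = 0.031.

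**Section 11.0**
- State that the interval for a group's average change uses the subject as the unit.
- Reconcile this with the reference to exact methods. One way is a t interval on the subject-level changes for the mean (multiplier 2.776 at n = 5, 4.303 at n = 3), keeping exact intervals for the per-subject differences.

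A table of illustrative half-widths is optional. If included, its SD must be labelled as assumed and as the total SD of observed subject-level changes, so that counting error is not added twice.

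The cost is wording in two sections. The precision shown for the Day 7 change becomes less favourable. The sample size, procedures and planned tests do not change.
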